9.0 Confidentiality, Privacy and Data Management

See the Research Data Plan Review Form

10.0 Data and Safety Monitoring Plan

Not applicable

11.0 Risks

Risk of loss of confidentiality

12.0 Potential Benefits to Subjects and Others

12.1 Potential Benefits to Subjects

None

12.2 Potential Benefits to Others

Accurate correction of astigmatism in patients undergoing femtosecond laser-assisted cataract surgery with astigmatic keratotomy is vital for patients to achieve spectacle independence. While there is a universal LRI calculator readily available to the refractive cataract surgeon, a similar calculator does not exist for AKs. A validated calculator to determine AK parameters would potentially allow for more patients undergoing femtosecond laser-assisted cataract surgery with astigmatic keratotomy to achieve spectacle independence.

13.0 Sharing Results with Subjects

Not applicable

14.0 Subject Stipend (Compensation) and/or Travel Reimbursements

Subjects will receive a thirty dollar gift card for participating in the study.

15.0 Economic Burden to Subjects

15.1 Costs

The subjects will not be responsible for any research-related costs (data collection from standard of care procedures and the one month follow-up research visit) for participating in the research.

15.2 Compensation for research-related injury

Not Applicable: no greater than minimal risk (loss of confidentiality) research.

16.2 Feasibility of recruiting the required number of subjects

The study team has access to approximately 10-20 potential subjects per week. At a minimum, 25% of subjects (4-5 per week) would need to be recruited in a one year period to reach the required number of participants for the desired study power.

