3.0 Inclusion and Exclusion Criteria

3.1 Inclusion Criteria

- Age: ≥18 years of age
- Sex: male or female
- Patients who are planned to undergo femtosecond laser-assisted cataract surgery with astigmatic keratotomy at the Schein Ernst Mishra Eye clinic within the next 60 days of their cataract consultation visit. Subjects with planned single or bilateral cataract eye surgeries are eligible. Planned opposite eye surgery must be within 2-4 weeks of first cataract surgery.
- Fluent in written and spoken English

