7.2 Study Procedures

7.2.1 Visit 1 or Day 1 or Pre-test, etc. (format accordingly)

Pre-operative visit: Inclusion/exclusion criteria will be assessed. Consent will be obtained from eligible subjects who wish to participate in the study. Demographic and baseline characteristics will be recorded. Pre-operative biometry, refraction, and corneal hysteresis data will be collected.

7.2.2 Visit 2

Day of surgery: Data from the femtosecond laser will be collected, including the various laser parameters that are used to make the astigmatic keratotomies and clear corneal incisions.

7.2.3 Visit 3

Day of surgery for contralateral eye: Data from the femtosecond laser will be collected, including the various laser parameters that are used to make the astigmatic keratotomies and clear corneal incisions.

7.2.4 Visit 4 or post-operative month #1 visit (1 month after 2nd operative procedure)

Post-operative month 1 visit: One-month post-operative IOL master, autorefraction, manifest refraction, and uncorrected visual acuity will be collected.

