7.3 Duration of Participation

The individual subject will participate in the study from the time consent is obtained at their pre-operative visit, through their femtosecond laser-assisted cataract surgery with astigmatic keratotomy on both eyes, and until their one-month post-operative visit.

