8.0 Subject Numbers and Statistical Plan

8.1 Number of Subjects

300

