8.2 Sample size determination

Eyes may have with-the-rule, against-the-rule, and oblique astigmatism. Corneas with varying forms of astigmatism will respond differently to the AKs; thus it is necessary to have a sufficient number of eyes to produce results for all forms of astigmatism. Approximately 50% of eyes have against-the-rule astigmatism, 30% with-the-rule, and 20% oblique. 20% of 300 eyes = 60, which was felt to be the minimum number to produce meaningful results for this group.

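### Section 8.1 sets 300 subjects but 8.2 derives 300 eyes; if subjects are meant, the minimum recruitment rate in 16.2 falls 40–92 short in its stated year

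*Combined protocol and SAP*

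**What the plan says.** All references are to the combined protocol and SAP.

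- **Target.** Under the heading "8.1 Number of Subjects" there is one figure, 300, and no other text.
- **Justification (8.2).** The section splits eyes into against-the-rule (50%), with-the-rule (30%) and oblique (20%) and concludes: "20% of 300 eyes = 60, which was felt to be the minimum number to produce meaningful results for this group".
- **Eyes per subject (3.1).** "Subjects with planned single or bilateral cataract eye surgeries are eligible".
- **Expected path (7.2.3, 7.2.4, 7.3).** Visit 3 is the "Day of surgery for contralateral eye", the outcome visit is timed "1 month after 2nd operative procedure", and participation is described as running "through their femtosecond laser-assisted cataract surgery with astigmatic keratotomy on both eyes".
- **Recruitment (16.2).** "The study team has access to approximately 10-20 potential subjects per week". Then: "At a minimum, 25% of subjects (4-5 per week) would need to be recruited in a one year period to reach the required number". The sentence goes on to call these participants and to link the number to a desired power.

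No section states what share of subjects is expected to contribute two eyes.

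**The concern.** The same number, 300, counts people in 8.1 and eyes in 8.2. The two counts agree only if every subject contributes exactly one eye, and 3.1 and 7.2 show that this is not the plan. The section that should confirm the target, 16.2, counts people, and its rate does not multiply up to 300 people in the year it names.

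At stake is when enrolment stops. Read as subjects, the target could bring in twice as many eyes as 8.2 asks for. Read as eyes, it could be reached with half the people that 8.1 announces. The expected size of the oblique group, which drives the target, moves with the reading, and so does the recruitment rate that the team should hold itself to.

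**Working it through.** **Inputs from the protocol.** Target 300 (8.1, 8.2); oblique share 20% (8.2); one or two eyes per subject (3.1); flow of 10–20 potential subjects per week, and a minimum of 4–5 recruited per week for one year (16.2). **Assumptions, not in the protocol.** One year is 52 weeks; b is the share of subjects contributing two eyes; r is the correlation between fellow eyes.

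**1. The plan's own figure.** 0.20 × 300 = 60 eyes. The step in 8.2 reproduces, in eyes.

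**2. Subjects against eyes.** Eyes from 300 subjects = 300 × (1 + b), which runs from 300 (b = 0) to 600 (b = 1). Subjects for 300 eyes = 300 / (1 + b), which runs from 300 down to 150.

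**3. The rate in 16.2.** 4 × 52 = 208 and 5 × 52 = 260 subjects. The length assumed for the year hardly matters: 50 weeks gives 200–250.

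**4. If 300 means subjects.** Shortfall: 300 − 260 = 40 (40/300 = 13%) to 300 − 208 = 92 (92/300 = 31%). Rate needed: 300/52 = 5.8 per week, which is 5.77/20 = 29% to 5.77/10 = 58% of the flow. Time needed at 5 or 4 per week: 300/5 = 60 or 300/4 = 75 weeks, that is 8 or 23 weeks beyond 52.

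**5. If 300 means eyes.** The rate suffices when (subjects recruited) × (1 + b) is at least 300. At 5 per week, b ≥ 300/260 − 1 = 15%. At 4 per week, b ≥ 300/208 − 1 = 44%.

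**6. Both readings over a range of b.**

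| Assumed b | Eyes from 4–5 subjects per week, 52 weeks | Subjects for 300 eyes (rate per week) | Expected oblique eyes from 300 subjects |
|---|---|---|---|
| 0% | 208–260 | 300 (5.8) | 60 |
| 25% | 260–325 | 240 (4.6) | 75 |
| 50% | 312–390 | 200 (3.8) | 90 |
| 100% | 416–520 | 150 (2.9) | 120 |

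On the eyes reading the expected oblique number is 60 in every row. All these are enrolled eyes, before withdrawals (3.3.2) and the acuity exclusion (8.3).

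**7. Information, as opposed to eyes.** For a simple mean, k single-eye and m bilateral subjects count as (k + 2m)² / (k + 2m(1 + r)) independent eyes. At an assumed r of 0.5:

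- 300 bilateral subjects: 600²/(600 × 1.5) = 400.
- 200 subjects, half bilateral: 300²/(100 + 200 × 1.5) = 225.
- 150 bilateral subjects: 300²/(300 × 1.5) = 200.

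The discount applies whichever unit is chosen.

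**The case against.** The strongest reply is that 300 plainly means eyes. Section 8.2 is the only reasoning offered and it works in eyes, while 7.2.3, 7.2.4 and 7.3 treat surgery on both eyes as the usual course. If half the subjects were bilateral, 4 per week would already give 312 eyes, and 16.2 would need no new rate. This largely stands: a reader might infer that 16.2 is simply wrong, and the documents do not support that, because the shortfall is certain only if 300 means subjects. But the reply depends on a bilateral share that the protocol never states, and it concedes that 8.1 is mislabelled.

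A second reply is that little harm follows. Each subject brings at least one eye, so 300 subjects yields at least 300 eyes, and either reading meets the minimum of 60 expected oblique eyes before losses. The study is observational (7.1), and enrolment does not alter the surgical plan. That also stands, and it limits the weight of the point.

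Two other inferences should be resisted. One is that recruitment is infeasible: 5.8 per week lies within the stated flow of 10–20. The other is that the study is underpowered: 8.2 and 8.3 give no significance level, effect size, standard deviation or power, so there is nothing to fall short of. Nor is much made of the 25% in 16.2. A rate of 4–5 is 25% of a flow of 16–20, which lies inside the approximate range given.

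**Conclusion.** The unit mismatch between 8.1 and 8.2 is definite. It leaves the number of eyes uncertain by up to a factor of two, although the uncertainty in information is smaller once fellow eyes are allowed to correlate. The recruitment shortfall is conditional: 13–31% on the subjects reading, which is how 8.1 and 16.2 are worded. On the eyes reading it disappears if the bilateral share is at least about 15% (at 5 per week) or 44% (at 4 per week). The protocol does not show which reading was intended, so neither an error in the rate nor its adequacy is proven. At least one of 8.1 and 16.2 needs correcting or completing. The result rests on a 52-week year and on no other assumption; b and r only illustrate the range.

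**What to change.** The investigator should choose one unit and use it in 8.1, 8.2 and 16.2. This is a design decision, because it sets the size of the study.

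- **If subjects:** restate 16.2 as about 5.8 per week (29–58% of a flow of 10–20), or as 60–75 weeks at 4–5 per week, and give in 8.2 the expected number of eyes. The cost is a higher stated rate or a recruitment period 8–23 weeks longer than a year.
- **If eyes:** restate 8.1 as 300 eyes with the implied number of subjects, 300/(1 + b), at a stated and justified b, and give in 16.2 the rate that follows. At b = 50%, for example, this is 200 subjects and 3.8 per week, or 19–38% of the flow (3.85/20 to 3.85/10). The cost is a lower stated number of subjects, by up to half, and correlated fellow eyes that carry less information than 300 independent eyes would.

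In either case, remove from 16.2 the reference to a desired power and point instead to the judgement-based minimum in 8.2. Neither option requires more than the 300 subjects already stated.

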16.3 PI Time devoted to conducting the research

The PI has 20% academic time and will be contributing half of this to research activities, for a total percentage effort of 10%.

16.4 Availability of medical or psychological resources

Not applicable

16.5 Process for informing Study Team

Team members will meet with the PI periodically during the course of the study to ensure proper training on study protocol and duties.

17.0 Other Approvals

17.1 Other Approvals from External Entities

Not applicable

17.2 Internal PSU Committee Approvals

Check all that apply:

- Anatomic Pathology – Hershey only – Research involves the collection of tissues or use of pathologic specimens. Upload a copy of HRP-902 - Human Tissue For Research Form on the “Supporting Documents” page in CATS IRB. This form is available in the CATS IRB Library.
- Animal Care and Use – All campuses – Human research involves animals and humans or the use of human tissues in animals
- Biosafety – All campuses – Research involves biohazardous materials (human biological specimens in a PSU research lab, biological toxins, carcinogens, infectious agents, recombinant viruses or DNA or gene therapy).
- Clinical Laboratories – Hershey only – Collection, processing and/or storage of extra tubes of body fluid specimens for research purposes by the Clinical Laboratories; and/or use of body fluids that had been collected for clinical purposes, but are no longer needed for clinical use. Upload a copy of HRP-901 - Human Body Fluids for Research Form on the “Supporting Documents” page in CATS IRB. This form is available in the CATS IRB Library.
- Clinical Research Center (CRC) Advisory Committee – All campuses – Research involves the use of CRC services in any way.
- Conflict of Interest Review – All campuses – Research has one or more of study team members indicated as having a financial interest.
- Radiation Safety – Hershey only – Research involves research-related radiation procedures. All research involving radiation procedures (standard of care and/or research-related) must upload a copy of HRP-903 - Radiation Review Form on the “Supporting Documents” page in CATS IRB. This form is available in the CATS IRB Library.

- IND/IDE Audit – All campuses – Research in which the PSU researcher holds the IND or IDE or intends to hold the IND or IDE.
- Scientific Review – Hershey only – All investigator-written research studies requiring review by the convened IRB must provide documentation of scientific review with the IRB submission. The scientific review requirement may be fulfilled by one of the following: (1) external peer-review process; (2) department/institute scientific review committee; or (3) scientific review by the Clinical Research Center Advisory committee. NOTE: Review by the Penn State Hershey Cancer Institute Scientific Review Committee is required if the study involves cancer prevention studies or cancer patients, records and/or tissues. For more information about this requirement see the IRB website at: <http://www.pennstatehershey.org/web/irb/home/resources/investigator>

18.0 Multi-Site Research

Not applicable

19.0 Adverse Event Reporting

19.1 Reporting Adverse Reactions and Unanticipated Problems to the Responsible IRB

In accordance with applicable policies of The Pennsylvania State University Institutional Review Board (IRB), the investigator will report, to the IRB, any observed or reported harm (adverse event) experienced by a subject or other individual, which in the opinion of the investigator is determined to be (1) unexpected; and (2) probably related to the research procedures. Harms (adverse events) will be submitted to the IRB in accordance with the IRB policies and procedures.

20.0 Study Monitoring, Auditing and Inspecting

20.1 Auditing and Inspecting

The investigator will permit study-related monitoring, audits, and inspections by the Penn State quality assurance program office(s), IRB, the sponsor, and government regulatory bodies, of all study related documents (e.g., source documents, regulatory documents, data collection instruments, study data etc.). The investigator will ensure the capability for inspections of applicable study-related facilities (e.g., pharmacy, diagnostic laboratory, etc.).

21.0 Future Undetermined Research: Data and Specimen Banking

Not applicable

